The purpose of the current study is to prospectively analyze two groups of patients treated for rotator cuff repair with and without a flowable pECM to determine if a significant reduction in pain and opioid consumption as measured in morphine equivalent units is demonstrated within the first 6 weeks of surgery. Furthermore, patients will be compared in regard to early range of motion and patient reported outcomes to determine if a difference is present when the ECM is utilized within the first 6 months of surgery. This is the first double blinded prospective series in the shoulder literature to date looking at a pECM graft for pain reduction and improved range of motion perioperatively.

Study Objectives

Utilizing a prospective randomized controlled trial, the aim of this study is to assess modulation of post-operative pain and narcotic use when a placental-derived extracellular matrix is injected into the bed of the repair following outpatient rotator cuff repair surgery. Furthermore, this study aims to determine if the addition of pECM influences patient reported outcomes and influences early postoperative range of motion.

Primary Aims & Objective

Aim 1a: To assess post-operative narcotic consumption (measured in morphine equivalent units) between patients treated with flowable placental-derived pECM compared to those patients undergoing rotator cuff surgery.

Hypothesis: Narcotic consumption (measured in morphine equivalent units) will be reduced in patients treated with an extracellular matrix graft as compared to those patients undergoing rotator cuff surgery without.

Objective: Utilizing a prospective randomized controlled trial, narcotic use will be measured for 12-hour increments for a total of 7 post-operative days (PODs) then once on POD 14, 21, 28, and 42. Consumption will be measured by the number of tablets ingested and converted to morphine equivalent units and compared between the two treatment groups.

Aim 1b: To determine if flowable placental-derived pECM decreases patient-reported post-operative VAS pain in patients undergoing outpatient rotator cuff surgery

Hypothesis: There will be a decrease in VAS pain for up to 6 weeks post-operatively among participants who receive pECM, as compared to the control group (no pECM).

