Objective: Utilizing a prospective randomized controlled trial, post-operative patient-reported VAS pain (on a scale of 0-10) will be collected 2 times per day (every 12 hours) for 7 post-operative days (PODs); then an average score collected on POD 14, POD 21, POD 28, and POD 42. Scores will be averaged and compared between the two treatment groups for the first 7 days, 2 week, 3rd week, 4th week and 6th week postoperatively.

Secondary Aims & Objectives

Aim 2a: To assess patient-reported outcomes and early range of motion (measured in morphine equivalents) in patients treated with flowable placental-derived pECM compared to patients injected with saline control.

Hypothesis: There will be improved patient reported outcomes and early range of motion measured at 6 weeks and 3 months and 6 months postoperatively in patients receiving and extracellular matrix injection following outpatient rotator cuff surgery.

Objective: Utilizing a prospective randomized controlled trial, patient reported outcomes as measured by American Shoulder and Elbow Score, Simple Shoulder Test and SANE scores and range of motion (External rotation, internal rotation and forward flexion) will be collected preoperatively and at 2 weeks (external rotation), 6 weeks (all) , 3 months (all) and 6 months (all) postoperatively. Scores and range of motion measurements will be averaged and compared for differences between the two groups.

Study Design

The study design is a randomized double-blind randomized controlled trial.

Research Design

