Patient IQ is password protected and HIPPA compliant data collection system. Patients upon enrollment will be assigned an ID to allow for data tracking within the application. The application does not have access to other personal information on the patient's electronic device. Primary data will be collected via the web-based system and stored electronically and encrypted under password protection. The principal investigator will only have access to the database. At the conclusion of the study, the data will be exported to a password-protected encrypted Excel file on a password-protected computer. Once the data have been checked for accuracy and prior to statistical analysis, patient identifiers will be removed from the data set. The de-identified password-protected Excel spreadsheet will be provided to a statistician who will import the file into SPSS for analysis.

Study Agent, Device, and/or Intervention Description

The pECM graft administered at completion of the surgery is the intervention in this study. Study participants will be randomized into one of two groups. The treatment groups are listed below:

Group 1 (Control)	Group 2
Standard rotator cuff repair and no pECM injection	Rotator cuff repair and 2cc of pECM injection into perimeter of repair

Sample Size

For an analysis of variance (ANOVA) test, a sample size of 28 participants per group would be required, given an effect size of $f=0.30$ a power of 80%, and a two-tailed alpha level of 0.05. However, to account for 20% subject attrition, a total of 35 patients per group will be enrolled, yielding a total of 70 participants.

Subject Selection

Patients who meet the following criteria will be included in the study:

Inclusion Criteria

1. Age 18 and older
2. Primary diagnosis of rotator cuff tear
3. Able to provide informed consent
4. Is willing and able to accept text messages

Patients who meet the following conditions will be excluded from participation:

Exclusion Criteria

1. Older than 55 years old.
2. Pregnancy.
3. Known narcotic or alcohol abuse (< 3 months)
4. Revision rotator cuff surgery
5. Current narcotic regimen or contract with pain management specialist

Study Outcome Measures (Endpoints)

Primary Endpoint: Patient-reported post-operative VAS pain (on a scale of 0-10), measured post operatively, in 12-hour increments, for a total of 7 days postoperatively and then once per day on POD 14, 21, 28 and 42.

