Patients will be prompted via text message to provide VAS pain every 12 hours for the first 7 days and then once per day at later timepoints. If a response text message is not received, a phone call will be made to obtain the information. Patients who do not have a smart phone will receive a phone call or keep a personal log of VAS pain.

Secondary Endpoint: Patient-reported post-operative opioid use (converted to morphine equivalents), collected post operatively, in 12-hour increments for the first 7 days and then once per day on POD 14, 21, 28 and 42.

Patients will be prompted via text message to provide the amount of narcotics (number of pills converted to morphine equivalents) taken over the course of the previous 12 hours. If a response text message is not received, a phone call will be made to obtain the information. Patients who do not have a smart phone will receive a phone call or keep a personal log of narcotic use.

Study Procedures

Subject Recruitment and Screening

Participants will be recruited from the clinical practice of [name]. Patients who present for an office visit and are diagnosed with a rotator cuff tear requiring outpatient surgical intervention will be screened for eligibility for participation in the study. If a patient is eligible for the study, [name] will discuss the study with the patient and obtain informed consent during the routine office visit.

Randomization

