6 months	Office Exam	VAS; ER (neutral and scapular/IR-scapular/FF; ASES; SANE; SST

The enrollment period for study participation is anticipated to last for 12 months only for data analysis.

Specimen Collection, Preparation, Handling and Shipping

N/A

Statistical Analysis Plan

After data checking and validation are completed, the analysis of the data will begin with examination of the distribution of each of the study variables. In this process, outliers will be identified and evaluated for inclusion in the final study database. Appropriate summary statistics will be calculated. Means and standard deviations will be reported for normally distributed continuous variables, a median and range will be tabulated for continuous variable that are not normally distributed, and frequencies and percentages will be provided for categorical variables. The remainder of the analysis will correspond to the specific aims provided above.

Specific Aims 1a-b:

To determine if there is a difference in patient-reported post-operative narcotic use (measured in morphine equivalents) among two groups.

If data are normally distributed, analysis of variance (ANOVA) with Tukey's HSD pairwise comparisons will be used to compare narcotic use (converted to morphine equivalents) between the three groups at each PODs. Cumulative narcotic use during all PODs will also be compared between groups. If data are not normally distributed, then Kruskal-Wallis with Dunn's multiple comparisons tests will be used.

To determine if there is a difference in mean VAS pain between the control group and ECM group postoperatively.

If data are normally distributed, analysis of variance (ANOVA) with Tukey's HSD pairwise comparisons will be used to compare VAS pain between the two groups at each PODs 1-7, 14, 21, 28 and 42. If data are not normally distributed, then Kruskal-Wallis with Dunn's multiple comparisons tests will be used.

Specific Aim 2:

To determine if there is a difference in clinical and functional outcomes of patients with rotator cuff tears treated with the nanofiber scaffold compared to those treated without.

If data are normally distributed, independent t-tests will be used to compare VAS Pain, SANE, V-12, ASES, and ROM measures between the control and intervention groups at each preoperative and postoperative timepoint. If data are not normally distributed, then Mann-Whitney U tests will be performed.

Potential Risks and Benefits

Potential Risks

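### No single test answers the primary question: opioid use is ranked both primary and secondary, and VAS pain has no primary time point or summary and no adjustment across days

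*Combined protocol and SAP*

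**What the plan says.** **Ranking of the endpoints.** Under Primary Aims & Objective, opioid use comes first: "Aim 1a: To assess post-operative narcotic consumption (measured in morphine equivalent units"). VAS pain follows as Aim 1b. Study Outcome Measures (Endpoints) ranks them differently: "Primary Endpoint: Patient-reported post-operative VAS pain (on a scale of 0-10"), then "Secondary Endpoint: Patient-reported post-operative opioid use (converted to morphine equivalents").

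**Definition of the VAS endpoint.** The Endpoints section lists when VAS is collected: every 12 hours for 7 days, then on POD 14, 21, 28 and 42. It names no decisive time point or summary. The Aim 1b hypothesis spans the whole period: "There will be a decrease in VAS pain for up to 6 weeks post-operatively among participants who receive pECM".

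**Analysis of VAS.** The Aim 1b objective calls for mean scores, to be "compared between the two treatment groups for the first 7 days, 2 week, 3rd week, 4th week and 6th week postoperatively". That is five comparisons. The Statistical Analysis Plan, Specific Aims 1a-b, says that ANOVA with Tukey's HSD, or Kruskal-Wallis with Dunn's test for non-normal data, "will be used to compare VAS pain between the two groups at each PODs 1-7, 14, 21, 28 and 42". That is 11 comparisons.

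**Analysis of opioid use.** The same SAP section compares opioid use on each POD and adds a cumulative comparison. It refers to three groups, although the trial has two.

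**Significance level.** The only alpha is in the Sample Size section: "a power of 80%, and a two-tailed alpha level of 0.05". It belongs to one ANOVA with no endpoint or time point attached.

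**The concern.** A confirmatory trial needs one result, fixed in advance, that will be taken as the answer. Here the label of primary endpoint picks a variable but not a test. Five or 11 VAS results could each be presented as the primary finding. Because the Aims and the Endpoints disagree, an opioid result could be presented that way too.

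The documents contain no success rule, testing order, alpha split or adjustment across days. If results were mixed, for example significant on two days of 11, the plan would not say whether the primary hypothesis was supported. The choice could then be made after seeing the data, and the chance of a false claim would exceed the 5% implied by the sample-size paragraph.

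**Working it through.** **1. Inputs.** From Sample Size: two-sided alpha 0.05 and 28 evaluable patients per group. The attrition step reproduces: 28/(1 − 0.20) = 35 per group, 70 in total. The 28 itself does not follow from f = 0.30 with two groups, which needs 45 per group. That is a separate matter. A t-test holds its 5% level at either size, so the error rates below do not turn on it. The between-day correlation is not in the documents and is varied over an assumed range.

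**2. Number of VAS tests.** SAP: 7 (POD 1-7) + 4 (POD 14, 21, 28, 42) = 11. This assumes that the two daily readings are combined, which the SAP does not state. Testing each reading would give 7 × 2 + 4 = 18. Aims: 5. Only the first of those periods pools several readings; the other four are one score each.

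**3. Do Tukey or Dunn help?** Both adjust for the number of group pairs. Two groups make one pair. With 2 × 28 − 2 = 54 degrees of freedom, the Tukey critical value divided by √2 is 2.0049, and the ordinary t critical value is 2.0049. Dunn's test likewise has only one pair to adjust for.

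**4. Independent days, closed form.** Chance of at least one false positive = 1 − (1 − 0.05)^m.

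- m = 11: 1 − 0.95^11 = 43.1%
- m = 5: 1 − 0.95^5 = 22.6%
- m = 18: 1 − 0.95^18 = 60.3%

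**5. Correlated days, simulation.** No true effect, 28 per group, each test at two-sided 0.05. The t-test rows use normal outcomes and 40,000 replicates. The Kruskal-Wallis row uses 20,000 replicates of whole-number 0-10 scores (assumed latent mean 4, SD 2.5). Chance of at least one false positive (%):

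| Between-day correlation | 0 | 0.3 | 0.5 | 0.7 | 0.9 |
|---|---|---|---|---|---|
| 11 days, t-test, constant correlation | 43.1 | 38.0 | 30.7 | 22.3 | 13.2 |
| 11 days, t-test, correlation ρ^(days apart) | – | 42.5 | 40.8 | 37.2 | 29.1 |
| 11 days, Kruskal-Wallis, constant correlation | 43.4 | 38.2 | 31.0 | 23.7 | 14.2 |
| Five periods, POD 1-7 averaged | 22.5 | 20.3 | 17.2 | 13.8 | 9.5 |
| 11 days, false result favouring pECM only | 24 | 19 | 16 | 11 | 7 |
| Five periods, false result favouring pECM only | 12 | 10 | 9 | 7 | 5 |

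In the five-period rows the correlation is between days. If it is instead held constant between the five period scores, the two-sided figures are about 23/21/18/15/10%.

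**6. One summary, tested once.** The mean of POD 1-7, or the mean of all 11 days, gives 4.8-5.2% in every setting.

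**7. Why not just adjust across days?** Bonferroni would control the error but at a cost in power. At the plan's f = 0.30 and 28 per group, power is 59.7% for one test at 0.05, 34.5% at 0.05/5 = 0.01, and 25.0% at 0.05/11 = 0.00455.

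**The case against.** **The Endpoints section does rank the outcomes.** It does, with VAS first and opioid use second. The conflict with the Aims remains, and the ranking still attaches no test to VAS.

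**The SAP may mean the same five blocks as the Aims.** Its introduction says that the analysis follows the aims, and it speaks of mean VAS pain. The word *each* favours 11 separate days, but the wording can be called ambiguous. This does not rescue the plan: five unadjusted tests also exceed 5%, and the ambiguity is itself part of the problem.

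**43% is an upper figure, not an estimate.** Correct, among the 11-day figures. It needs independent days and a rule that any significant day counts, and the documents state no such rule. Scores from the same patients will be correlated. It also counts differences in either direction, whereas the hypothesis is a reduction with pECM. Counting only false results that favour pECM roughly halves the figures. Even so, 7% (11 days) or 5% (five periods) at correlation 0.9 compares with 2.5% for a single test.

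**Another cure exists.** Two primary endpoints with a split alpha would also be valid, since the stated purpose names pain and opioid use together. At 0.025 each, power with 28 per group falls from 59.7% to 48.1% at f = 0.30.

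**The three-groups wording is editorial.** Agreed. The same section also says two groups. It should be corrected but carries no weight here.

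**Conclusion.** The concern holds. The Aims and Endpoints conflict on the rank of opioid use, the VAS endpoint is a schedule without a decisive summary, the two descriptions of the VAS analysis do not match, and nothing adjusts across days.

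Followed literally, the SAP leaves the primary question to at least 11 unadjusted tests. The chance of at least one false-positive VAS result is then 13% to 43%, depending on the between-day correlation, against a nominal 5%. On the five-period reading it is about 10% to 23%. These figures assume no true effect, 28 per group, each test at two-sided 0.05, and correlations from 0 to 0.9 that the documents do not supply. They cover the Aim 1b tests only. The opioid tests, and the repeat VAS comparisons under Specific Aim 2, enlarge the set.

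The lack of a decisive test does not depend on any of these assumptions. It should be settled before unblinding.

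**What to change.** Before unblinding, make the Aims, Endpoints and SAP agree on the following.

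1. **One primary endpoint.** VAS pain, following the Endpoints section, with opioid use secondary throughout.
2. **One VAS summary per patient, compared once** between the two groups at two-sided 0.05. The sponsor should choose and justify it. Mean VAS over POD 1-7, the first period in the Aim 1b objective, is one suitable choice. An average over 6 weeks is another, since the hypothesis runs that long and the background points to pain beyond 72 hours. A 6-week average needs stated weights: a plain mean of the 11 days gives the first week 7/11 = 64% of the weight. State also how the two daily readings are combined.
3. **Opioid use tested second**, for example in fixed order after VAS, with one named summary. The SAP already has a cumulative total over all recorded days. However, the Endpoints section asks for pills "taken over the course of the previous 12 hours", and after POD 7 this is asked on only four isolated days, so that sum is not total consumption. The cumulative total over POD 0-7, recorded in consecutive 12-hour slots, is a cleaner choice.
4. **Remaining day-by-day comparisons** reported as descriptive, with confidence intervals.
5. **Wording.** Remove the reference to three groups and the Tukey and Dunn procedures.

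The cost is wording in three sections, and day-specific p-values lose confirmatory status. No new data are needed.

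### The primary VAS pain comparison uses no baseline information, so it gives up precision that a prespecified baseline covariate could recover; the size of the gain is unknown

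*Combined protocol and SAP*

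**What the plan says.** - **Endpoint.** Study Outcome Measures names pain as primary: "Primary Endpoint: Patient-reported post-operative VAS pain (on a scale of 0-10), measured post operatively, in 12-hour increments". The aims section also lists narcotic use (Aim 1a) as a primary aim, but the endpoint section makes opioid use secondary. VAS is treated as primary here.
- **Analysis.** Under Specific Aims 1a-b, ANOVA with Tukey's HSD "will be used to compare VAS pain between the two groups at each PODs 1-7, 14, 21, 28 and 42". The alternative is also group-only: "If data are not normally distributed, then Kruskal-Wallis with Dunn's multiple comparisons tests will be used". No covariate, change score or baseline-adjusted model appears anywhere in the plan.
- **Baseline data.** The Aim 2a Objective states that ASES, SST, SANE and range of motion "will be collected preoperatively and at 2 weeks (external rotation), 6 weeks (all) , 3 months (all) and 6 months (all) postoperatively".
- **Preoperative VAS.** The Specific Aim 2 analysis would "compare VAS Pain, SANE, V-12, ASES, and ROM measures between the control and intervention groups at each preoperative and postoperative timepoint", so it assumes a preoperative pain score. The Aim 2a Objective does not list one. The table under Study Visits/Study Duration has no preoperative row, and its first pain record is at 8 pm on the day of surgery.
- **Allocation.** Research Design and Randomization describe a draw from 70 envelopes (35 per group) with no stratification.

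**The concern.** Patients who differ in shoulder pain and function before surgery may also differ in pain afterwards. In a group-only test, that between-patient variation stays in the error term. The envelope draw fixes the arm sizes but does nothing to balance preoperative pain. In the Aim 2 text, preoperative values are only compared between arms, which neither corrects an imbalance nor adds precision. The plan gives no reason for leaving the primary comparison unadjusted.

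At stake is the precision of the pECM effect on pain in a trial of 70 patients. If the baseline predicts the outcome, the same patients would give a narrower confidence interval and more power. A chance imbalance could also be accounted for in the estimate.

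**Working it through.** **Inputs.** From Sample Size: f = 0.30, two-tailed alpha 0.05, 80% power, 28 evaluable per group, 35 enrolled. For two equal groups d = 2f = 0.60. The within-group correlation (rho) between the preoperative covariate and postoperative VAS is not in the documents, so it is varied as an assumption.

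**The plan's own figure.** The attrition step reproduces: 28/(1 - 0.20) = 35. The 28 does not: a two-group ANOVA with f = 0.30 needs 45 per group for 80% power. That is a separate error. It matters here because it sets the starting point for the comparison below.

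**Unadjusted power, one comparison.** Noncentrality = d × sqrt(n/2) = 0.60 × sqrt(14) = 2.245, with 2n - 2 = 54 degrees of freedom. Power is 59.7% at 28 per group and 69.7% at 35.

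**Adjusted power.** With one baseline covariate, noncentrality = d/sqrt(1 - rho²) × sqrt(n/2), with 2n - 3 degrees of freedom. At n = 28 and rho = 0.3 this is 2.245/sqrt(0.91) = 2.353; at rho = 0.5 it is 2.245/sqrt(0.75) = 2.592.

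| rho | Residual variance, 1 - rho² | Power, 28 per group | Gain (points) | Power, 35 per group |
|---|---|---|---|---|
| unadjusted | 1 | 59.7% | – | 69.7% |
| 0.1 | 0.99 | 60.1% | 0.4 | 70.1% |
| 0.2 | 0.96 | 61.4% | 1.7 | 71.4% |
| 0.3 | 0.91 | 63.7% | 4.0 | 73.7% |
| 0.4 | 0.84 | 67.2% | 7.5 | 77.0% |
| 0.5 | 0.75 | 72.1% | 12.4 | 81.5% |

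If rho were exactly zero, the lost degree of freedom would cost almost nothing: 59.65% against 59.68% at 28 per group.

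**Chance imbalance.** In SD units, the standard error of the baseline mean difference at 28 per group is sqrt(2/28) = 0.267. A difference above 0.3 SD in either direction has a probability of about 26%. Only the fraction rho carries into the unadjusted estimate: a one-standard-error imbalance moves it by 0.3 × 0.267 = 0.08 SD at rho = 0.3, and by 0.5 × 0.267 = 0.13 SD at rho = 0.5. The unadjusted treatment difference itself has a standard error of 0.267 SD, which already includes this component. Imbalance and lost power are therefore one source of variance seen two ways and must not be added together.

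**The case against.** **The correlation is unknown and may be low.** The background text says regional techniques and longer-acting agents give relief for about 72 hours, and that later pain is largely inflammatory, from surgical tissue damage. Neither mechanism is preoperative shoulder pain. Of the 19 scheduled VAS records to POD 42, 15 fall on POD 0-7. This does not show that rho is low, but it rules out presenting any single value, such as 0.5, as the expected case. The objection stands as a limit on the size.

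**Preoperative VAS may not exist.** A reader might infer that the trial has a preoperative pain score in hand and ignores it. The documents do not support that. The only mention is in the Aim 2 analysis text, which also refers to a nanofiber scaffold and to V-12. Neither appears elsewhere in the plan, so the text may have been carried over from another study. The measurement has to be scheduled first. Preoperative ASES, however, is already planned.

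**The unadjusted test is not wrong.** A reader might also infer that the primary result would be biased or its type I error inflated. Neither follows. Under randomisation the group-only comparison is unbiased on average and holds its error rate.

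These points reduce the claim but do not defeat it: the change costs little, and power is practically never lower.

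**Conclusion.** The point holds as a matter of efficiency. The primary VAS comparison leaves baseline information unused, and a prespecified covariate would improve precision to an extent that the documents do not settle. With 28 per group and d = 0.60, the gain runs from 0.4 points of power at rho = 0.1 to 4.0 at 0.3 and 12.4 at 0.5. It may be smaller in the first 72 hours. The figures assume a linear relation, equal arms and a single comparison at the plan's two-sided 0.05.

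It would be tempting to read adjustment as a cure for the low power. It is not: with 28 per group, 80% is reached only at a rho of about 0.62. The shortfall (about 60% instead of 80%) comes from the sample-size calculation and has to be corrected there. The change is worth making, but its absence does not invalidate the trial.

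**What to change.** 1. Add one 0-10 VAS item to the preoperative assessment at which ASES, SST and SANE are taken, and add that assessment to the schedule table.
2. In Specific Aims 1a-b, prespecify before unblinding an ANCOVA (linear model) of postoperative VAS on treatment group and preoperative VAS. Apply it to each VAS comparison that the plan makes: the averages in the Aim 1b Objective and the timepoints in the Statistical Analysis Plan. Report the adjusted mean difference with its 95% CI for each, and keep the unadjusted ANOVA or Kruskal-Wallis as supportive.
3. Use one covariate for all patients. Fill isolated missing baseline values simply, for example with the overall mean. If preoperative VAS is not collected at all, use preoperative ASES for every patient. Do not put VAS for some patients and ASES for others into the same term.

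**Cost.** One questionnaire item, one model term and one degree of freedom, with no extra patients or visits. If the correlation proves low, little is gained. The fix does not choose a primary timepoint or summary, and it leaves the sample-size correction still to be made.

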This is a double-blinded study, thus, neither the surgeon nor the patient will know if a pECM injection is used. A total of 70 envelopes will be generated consisting of 35 with Group 1” (no pECM) and 35 with “Group 2” (pECM Injection). Envelopes will be sealed and randomly chosen prior to surgery. Once the envelope is opened to determine if pECM is to be injected, the name of the patient will be added to the envelope along with the treatment group, and the envelope will be sealed. The treatment group and name of patient will be kept confidential until completion of the study. Envelopes will be opened at end of study for data collection and analysis purposes with patient information deidentified. They will be stored in a locked container at the surgery center only accessible by the chief of staff. Patients will be blinded to the treatment as well as the treating surgeon. The physician assistant will not be blinded as she will administer the injection for the treatment group but will keep the information confidential. She will not participate in follow-up data collection of the patients in this study postoperatively.

Study Visits/ Study Duration

Participants enrolled in this study will be followed for a period of 6 months post-operatively. For the first week, twice per day (12-hour increments), patients will self-report VAS pain and indicate their narcotic use (number of tablets ingested). Data concerning pain and narcotic use will be collected via text message (or phone if patients fail to respond to text messages).

Post-operative day (POD)	Data Collection Time	Data to be Collected
POD 0	8PM	VAS; #pain pills used
POD1	8AM	VAS; #pain pills used
	8PM	VAS; #pain pills used
POD2	8AM	VAS; # pain pills used
	8PM	VAS; # pain pills used
POD3	8AM	VAS; # pain pills used
	8PM	VAS; # pain pills used
POD4	8AM	VAS; # pain pills used
	8PM	VAS; # pain pills used
POD5	8AM	VAS; # pain pills used
	8PM	VAS; # pain pills used
POD6	8AM	VAS; # pain pills used
	8PM	VAS; # pain pills used

POD7	8AM	VAS; # pain pills used
	8PM	VAS; # pain pills used
POD14 (2 weeks)	Office Exam	ER (neutral); ASES; SANE; SST
	8PM	VAS; # pain pills used
POD21 (3 weeks)	8PM	VAS; # pain pills used
POD28 (4 weeks)	8PM	VAS; # pain pills used
POD42 (6 weeks)	Office Exam	ER (neutral and scapular/IR- scapular/FF; ASES; SANE; SST
	8PM	VAS; # pain pills used
3 months	Office Exam	VAS; ER (neutral and scapular/IR-scapular/FF; ASES; SANE; SST

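### Separate tests at each timepoint, with no missing-data method, default to available cases; with up to 20% attrition this risks bias, mainly at the 3- and 6-month visits

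*Combined protocol and SAP*

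**What the plan says.** In the Statistical Analysis Plan, Specific Aim 2, "independent t-tests will be used to compare VAS Pain, SANE, V-12, ASES, and ROM measures between the control and intervention groups" at every preoperative and postoperative timepoint, with Mann-Whitney U tests if the data are not normal. Under Specific Aims 1a-b, ANOVA (Kruskal-Wallis if not normal) is used to "compare VAS pain between the two groups at each PODs 1-7, 14, 21, 28 and 42". The objective under Aim 1b describes VAS differently: "Scores will be averaged and compared between the two treatment groups for the first 7 days, 2 week, 3rd week, 4th week and 6th week". It does not say how a missing report enters an average.

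Attrition appears once, under Sample Size: "to account for 20% subject attrition, a total of 35 patients per group will be enrolled". The documents name no repeated-measures model, imputation, analysis population or missing-data sensitivity analysis. The only rule on which values enter the analysis concerns outliers.

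Two features limit missing VAS reports. An unanswered text leads to a phone call (Research Design; Study Outcome Measures), and POD 1 to 7 have two reports a day (Study Visits/ Study Duration). No comparable follow-up is described for the office visits at 6 weeks, 3 months and 6 months.

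**The concern.** A t-test, ANOVA or rank test at one timepoint can use only patients who have a value there. Someone seen at 6 weeks and 3 months but not at 6 months adds nothing to the 6-month comparison, although the earlier scores show how that patient was recovering. Enrolling 35 instead of 28 per group replaces lost numbers. It does not restore the comparability that randomisation gave if those who leave differ from those who stay. The 6-month functional result could then rest on a selected subset, while the data that would correct part of the selection are collected and left unused.

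**Working it through.** **1. The plan's attrition figure.** 28 / (1 - 0.20) = 35 per group, so the inflation step reproduces. The base of 28 does not: a two-group ANOVA with f = 0.30, two-tailed alpha 0.05 and 80% power needs 45 per group. That is a separate issue and nothing below depends on it. At 20% loss a per-timepoint test uses about 28 + 28 = 56 of 70 patients, with a standard error of about sqrt(2/28) = 0.267 SD.

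**2. Inputs.** From the documents: 35 per arm, 20% attrition, and f = 0.30, which is d = 2 x 0.30 = 0.60 for two equal groups. Assumed, because the documents give nothing: correlation rho of 0.5 to 0.7 between an earlier and a later score; all of the 20% missing at the later visit; and a logistic probability of being missing, p(x) = 1/(1 + exp(-(c + bx))), where x is the earlier score in SD units, b is 1 to 2, and c is set to give 20% loss.

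**3. No true effect.** The observed patients' mean earlier score shifts by s = (integral of x(1 - p(x)) times the normal density) / 0.80. The later score shifts by rho x s. Solving for c gives s = -0.173, -0.227 and -0.262 for b = 1, 1.5 and 2.

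| Dropout pattern | Bias at the later visit | Simulated rejection at nominal 5% |
|---|---|---|
| Random | 0 | 5.0 to 5.1% |
| Score-related, same in both arms | 0 | 5.1 to 5.2% |
| One arm only, b = 1 to 2 | 0.5 x 0.173 = 0.09 to 0.7 x 0.262 = 0.18 SD | 6 to 10% |
| Opposite in the two arms, b = 1 | 2 x 0.5 x 0.173 = 0.17 to 2 x 0.7 x 0.173 = 0.24 SD | 10 to 15% |

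A simulation of 20,000 trials at b = 1.5 agrees. One-arm bias was 0.113 (rho 0.5) and 0.159 (rho 0.7), against 0.5 x 0.227 = 0.113 and 0.7 x 0.227 = 0.159.

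**4. A true effect of 0.60 SD at both visits, one identical rule in both arms, 20% lost overall.** The better-recovering arm now loses fewer patients. The observed difference is 0.60 less rho times the difference between the arms' shifts.

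| b | Loss, control / treated | Observed difference, rho 0.5 | rho 0.7 |
|---|---|---|---|
| 1 | 24% / 16% | 0.57 | 0.55 |
| 1.5 | 25% / 15% | 0.55 | 0.52 |
| 2 | 26% / 14% | 0.53 | 0.50 |

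The shrinkage is 0.03 to 0.10 SD. If c is instead set separately so that each arm loses exactly 20%, the simulated difference stays at 0.60, so the shrinkage comes from unequal loss.

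**5. Using the earlier visit.** The likelihood estimate of each arm's later mean is the observed later mean plus the regression slope times (mean earlier score of all patients minus mean earlier score of those observed later). Its simulated bias was at most 0.002 SD in every pattern in step 3, and it returned 0.60 under step 4. Under random dropout its standard error fell from 0.266 to 0.260 (rho 0.5, 2.3%) and from 0.269 to 0.256 (rho 0.7, 4.8%).

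**6. Model size.** An unstructured covariance has k(k + 1)/2 parameters. VAS on POD 1 to 7, 14, 21, 28 and 42 is 7 + 4 = 11 days, so 11 x 12/2 = 66 for 70 patients. Four office visits need 4 x 5/2 = 10, and three need 6.

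**The case against.** A reader might infer that the plan's 20% attrition turns into bias. The documents do not support that. Random dropout gives no bias, and the 28-to-35 inflation is meant to cover the loss of numbers. With no treatment effect, dropout that depends on the score in the same way in both arms gives none either. The patient and the surgeon are blinded and the unblinded physician assistant takes no part in follow-up data collection, so opposite dropout patterns are an extreme assumption. This stands as a limit on the size. It does not remove the risk, because step 4 needs no arm-specific rule: a working treatment and ordinary outcome-related dropout are enough.

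A reader might also take 20% as the loss at every timepoint, or think the plan says absent patients are dropped. The 20% is one overall allowance. Dropping is the default of the named tests combined with silence, not a stated rule. Phone calls and twice-daily reports mean that one missed text need not remove a patient from an early day, so the figures above should not be read across to POD 1 to 7.

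Finally, a mixed model has costs of its own: a covariance choice that 70 patients can support over 11 days, and normal theory for a 0 to 10 scale where the plan had rank-test fallbacks. Both stand and shape the fix.

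**Conclusion.** The concern holds as a conditional risk. The plan expects up to 20% loss, names no method for it, and chooses tests that ignore the other scores of patients who miss a visit. Under the assumed dropout slopes and correlations, the per-visit comparison is off by about 0.1 to 0.2 SD with score-related dropout in one arm, or a 0.60 SD effect is reported as about 0.50 to 0.57 SD. The one-arm bias is roughly a third to two thirds of the 0.267 SD standard error (0.09/0.267 to 0.18/0.267), which is moderate. The slopes, the correlations and the placing of the whole 20% at one visit are assumptions. The exposure is mainly in the Aim 2 measures at 3 and 6 months and is smaller for VAS to POD 42. Neither analysis corrects dropout that depends on scores never observed. This is a cheap improvement that should be made before the data are analysed.

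**What to change.** In the Statistical Analysis Plan:

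- **Aim 2 outcomes.** Make the main analysis of each outcome one repeated-measures mixed model including all randomised patients with any post-operative value. Use arm, visit and arm-by-visit as fixed effects, the preoperative value as covariate, and an unstructured within-patient covariance. Use only the visits at which the measure is scheduled: internal rotation and forward flexion start at 6 weeks. Whether ASES, SANE and SST start at 2 weeks must be reconciled, because the Aim 2a objective limits that visit to external rotation while the visit schedule adds the three scores.
- **VAS to POD 42.** Use the same model on daily means, with a preoperative value only if one is collected. Choose a parsimonious covariance, for example first-order autoregressive, or compound symmetry with robust standard errors. The later reports are 7 and 14 days apart, so an autoregressive form should allow for unequal spacing.
- **Reporting.** Give the arm difference and 95% CI at the timepoints already listed. Keep the per-timepoint t-tests or rank tests as a sensitivity analysis, which also covers non-normal scores.

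The cost is SAP wording and model fitting in SPSS, the software already named; no visits or patients are added. The model relies on data being missing at random given the observed scores, a weaker assumption than available-case tests need, and on an approximately normal model for a bounded scale. With a simplified VAS covariance it also relies on that structure being reasonable. The precision gain is small: a standard error about 2% to 5% lower under random dropout.
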